5.3 Efficacy, Pharmacokinetic, and Safety Assessments/Variables

5.3.1 Efficacy and Safety Measurements Assessed and Flow Chart

Study procedures described are listed in the following section of this protocol and are summarized in tabular format in [Appendix C](#) (Treatment Period) and [Appendix D](#) (Post-Treatment Period).

5.3.1.1 Study Procedures

Informed Consent

Signed study-specific informed consent will be obtained from the subject before any study procedures are performed. Details about how informed consent will be obtained and documented are provided in Section [9.3](#).

Medical History

A complete medical history, including history of tobacco, alcohol and drug use, will be taken from each subject at Screening Visit. The subject's medical history will be updated at the Study Day 1 Visit. This updated medical history will serve as the baseline for clinical assessment.

Physical Examination

A complete physical examination will be performed at visits specified in [Appendix C](#), or upon subject discontinuation. A symptom-directed physical examination may be performed at any other visit, when necessary.

The physical examination performed on Study Day 1 will serve as the baseline physical examination for clinical assessment. Any significant physical examination findings after the first dose will be recorded as adverse events.

Height will be measured only at Screening.

Vital Signs and Weight

Body temperature, blood pressure, pulse, and body weight will be measured at each study visit as specified in [Appendix C](#) and [Appendix D](#). Blood pressure and pulse rate should be measured after the subject has been sitting for at least 3 minutes. The subject should wear lightweight clothing and no shoes during weighing. The vital signs performed on Day 1 of the Treatment Period will serve as the baseline for clinical assessment.

12-Lead Electrocardiogram

A 12-lead resting ECG will be obtained at the visits indicated in [Appendix C](#). The ECG should be performed prior to blood collection.

The ECG will be evaluated by an appropriately trained physician at the site ("local reader"). The local reader from the site will sign, and date all ECG tracings and will provide his/her global interpretation as a written comment on the tracing using the following categories:

- Normal ECG
- Abnormal ECG – not clinically significant
- Abnormal ECG – clinically significant

Only the local reader's evaluation of the ECG will be collected and documented in the subject's source. The automatic machine reading (i.e., machine-generated measurements and interpretation that are automatically printed on the ECG tracing) will not be collected.

Clinical Laboratory Tests

Samples will be obtained at a minimum for the clinical laboratory tests outlined in [Table 5](#) at the visits indicated in [Appendix C](#) and [Appendix D](#).

Blood samples for serum chemistry tests should be collected following a minimum 8-hour fast prior to study drug intake (with the exception of the Screening Visit, which may be non-fasting). Subjects whose visits occur prior to the morning dose of study drug should be instructed to fast after midnight until the blood sample is collected in the morning and thereafter take their study medications with food. Subjects whose visits occur following the morning dose of study drug should be instructed to fast after breakfast until the study visit occurs. At the Study Day 1 visit, a fasting blood sample should be collected prior to the first dose of study drug. Blood samples should still be drawn if the subject did not fast for at least 8 hours. Fasting or non-fasting status will be recorded in the source documents and on the laboratory requisition. The baseline laboratory test results for clinical assessment for a particular test will be defined as the last measurement prior to the initial dose of study drug.

A central laboratory will be utilized to process and provide results for the clinical laboratory tests.

Instructions regarding the collection, processing, and shipping of these samples will be provided by the central laboratory chosen for this study. The certified laboratory chosen for this study is Covance. Samples will be sent to the following address:

Covance
[name]
[name]

Table 5. Clinical Laboratory Tests

Hematology	Clinical Chemistry	Additional Tests
Hematocrit	Blood Urea Nitrogen (BUN)	Anti-HCV Ab ^a
Hemoglobin	Creatinine	HCV RNA
Red Blood Cell (RBC) count	Total bilirubin	HCV genotype and subtype ^a
White Blood Cell (WBC) count	Direct and indirect bilirubin	HIV Ab ^a
Neutrophils	Alanine transaminase (ALT)	HIV RNA ^b
Bands, if detected	Aspartate transaminase (AST)	Hepatitis B Panel (Anti-HB ^c
Lymphocytes	Alkaline phosphatase	Total, Anti-HBs and HBsAg) ^c
Monocytes	Sodium	Anti-HBc IgM ^c
Basophils	Potassium	Anti-HBc Total ^c
Eosinophils	Calcium	Anti-HBs ^c
Platelet count (estimate not acceptable)	Inorganic phosphorus	Anti-HAV
Prothrombin Time/INR ^a	Total protein	IgM ^d
Activated partial thromboplastin time (aPTT)	Glucose	Anti_HAV Total ^d
	Albumin	Anti-HEV IgG ^d
	Chloride	Anti-HEV IgM ^d
	Bicarbonate	HEV RNA ^d
	Magnesium	HBV DNA ^e
	Gamma-glutamyl transferase (GGT)	Follicle Stimulating Hormone (FSH) ^f
		Urine and Serum Human Chorionic Gonadotropin (hCG) for females ^g
		Alpha2-macroglobulin ^h
		Haptoglobin ^h
		Apolipoprotein A1 ^h
		CD4, CD4% ^b
		CD8, CD8% ^b
		CD4:CD8 ^b

- a. Performed only at Screening.
- b. Only for known HCV/HIV co-infected subjects.
- c. Performed at Screening for all subjects and also performed for management of transaminase elevations (Section 6.1.7.1).
- d. Performed for management of transaminase elevation (Section 6.1.7.1).
- e. Performed at Screening for subjects who have occult HBV infection (positive Anti-HBc Total with negative HBsAg and Anti-HBs) and also performed for management of transaminase elevation (Section 6.1.7.1).
- f. Only performed if requested during screening for post-menopausal women <55 to verify FSH level if site does not have a previous result available.
- g. Required only for females of child bearing potential.
- h. Component of FibroTest and collected only if required for FibroTest calculation during the Screening Period.

For any laboratory test value outside the reference range that the investigator considers to be clinically significant:

- The investigator will repeat the test to verify the out-of-range value.
- The investigator will follow the out-of-range value to a satisfactory clinical resolution.
- A laboratory test value that requires a subject to be discontinued from the study or study drug or requires a subject to receive treatment will be recorded as an adverse event.

The management of laboratory abnormalities that may occur during the study is described in Section [6.1.7](#).

Pregnancy Testing

- WOCBP must have a negative serum pregnancy test result at Screening, and a negative urine pregnancy test at Study Day 1.
- Monthly pregnancy testing should be performed during treatment, including at the last dose and until 30 days of last study drug dose, as indicated in [Appendix C](#) and [Appendix D](#).
- Subjects with borderline pregnancy tests at Screening must have a serum pregnancy test \geq 3 days later to document continued lack of a positive result.
- Females of non-childbearing potential (either postmenopausal or permanently surgically sterile as defined in inclusion criterion #2) at Screening do not require pregnancy testing.

Concomitant Medication Assessment

Please refer to Section [5.2.3.2](#).

Hepatitis B, Hepatitis C Virus and HIV Screen

HBsAg, anti-HBc and anti-HBs, anti-HCV Ab and anti-HIV Ab testing will be performed at Screening. HBV DNA testing may be performed to exclude occult HBV infection.

The investigator must discuss any local reporting requirements to local health agencies with the subject. The site will report these results per local regulations, if necessary. The HIV results will not be reported by the central laboratory to the clinical database.

Liver Diagnostic Testing

Subjects will be considered to be without cirrhosis or with cirrhosis based on the definitions below:

Without Cirrhosis (F2 and F3)

- A liver biopsy within 24 months prior to or during Screening demonstrating the absence of cirrhosis, e.g., a METAVIR, Batts-Ludwig, Knodell, IASL, Scheuer, or Laennec fibrosis score of 2 – 3, Ishak fibrosis score of 3 or 4; or
- A FibroScan® score of 8.8 to < 12.5 kPa within \leq 6 months of Screening or during Screening period (FibroScan® must be approved by the local regulatory agency to qualify for entrance criteria); or
- A Screening FibroTest score of 0.49 to 0.72 (inclusive).¹⁸

With Cirrhosis (F4)

- Previous histologic diagnosis of cirrhosis on liver biopsy, e.g., METAVIR, Batts-Ludwig, Knodell, IASL, Scheuer, or Laennec fibrosis score of > 3, Ishak score of > 4 or on a liver biopsy conducted during Screening; or
- A FibroScan® score of \geq 12.5 kPa within \leq 6 months of Screening or during Screening period (FibroScan® must be approved by the local regulatory agency to qualify for entrance criteria); or
- A Screening FibroTest result that is \geq 0.73.

The result of the liver biopsy supersedes the results of FibroScan and FibroTest and result of FibroScan supersedes the results of FibroTest. At Screening, it is recommended that subjects should otherwise meet all other inclusion criteria and none of the exclusion criteria before undergoing a liver biopsy.

Subjects with cirrhosis will be defined as having compensated cirrhosis if the Child-Pugh Score at screening is ≤ 6 .

Child-Pugh Score and Category

All subjects with cirrhosis will have Child-Pugh scores assessed at screening. The Child-Pugh score uses five clinical measures of liver disease (3 laboratory parameters and 2 clinical assessments) as shown in [Table 6](#). Child-Pugh score will be determined at the visits indicated in [Appendix C](#) and [Appendix D](#).

Table 6. Child-Pugh Classification of Severity of Cirrhosis

Parameter	Points Assigned for Observed Findings		
	1	2	3
Total bilirubin, $\mu\text{mol/L}$ (mg/dL)	$< 34.2 (< 2)$	$34.2 - 51.3 (2 - 3)$	$> 51.3 (> 3)$
Serum albumin, g/L (g/dL)	$> 35 (> 3.5)$	$28 - 35 (2.8 - 3.5)$	$< 28 (< 2.8)$
INR	< 1.7	$1.7 - 2.3$	> 2.3
Ascites**	None	Slight	Moderate to severe
Hepatic encephalopathy*	None	Grade 1 or 2 (or suppressed with medication)	Grade 3 or 4 (or refractory)

Child-Pugh category A: 5 – 6 points; Child-Pugh category B: 7 – 9 points; Child-Pugh category C: 10 – 15 points.

* None: normal consciousness, personality, neurological examination, electroencephalogram.

Grade 1: restless, sleep disturbed, irritable/agitated, tremor, impaired handwriting, 5 cps waves.

Grade 2: lethargic, time-disoriented, inappropriate behavior, asterixis, ataxia, slow triphasic waves.

Grade 3: somnolent, stuporous, place-disoriented, hyperactive reflexes, rigidity, slower waves.

Grade 4: unarousable coma, no personality/behavior, decerebrate, slow 2 to 3 cps delta activity.

** None.

Slight ascites = Ascites detectable only by ultrasound examination.

Moderate ascites = Ascites manifested by moderate symmetrical distension of the abdomen.

Severe ascites = Large or gross ascites with marked abdominal distension.

Clinical Assessment of Hepatic Decompensation

A clinical assessment of hepatic encephalopathy and ascites, as defined in Exclusion Criterion #6, will be performed at Study Day 1 prior to dosing to confirm the subject has not progressed to hepatic decompensation since Screening for all subjects who have

compensated cirrhosis. Subjects who present symptoms and signs of hepatic decompensation, including assessment at Day 1 prior to receiving study drug, will neither be dosed nor enrolled into the trial.

Hepatocellular Carcinoma Screening: Liver Ultrasound

HCC screening will be required as a protocol-specified study procedure only at the Screening Visit and at the last Post-Treatment Study Visit, as indicated in [Appendix C](#) and [Appendix D](#), for subjects with compensated cirrhosis only. In-between those visits, HCC screening should be performed according to standard of care.

At the Screening Visit and at the last Post-Treatment Study Visit, subjects with compensated cirrhosis will be required to undergo a liver ultrasound to screen for HCC, unless the subject has a historical liver ultrasound, CT scan or MRI performed for HCC screening within 3 months prior to those visits, in which case the result of the historical ultrasound, CT scan or MRI will be used as the result for the Study Visit assessment. A positive ultrasound result suspicious of HCC will be confirmed with CT scan or MRI. Alternate methods of screening for HCC (i.e., CT scan or MRI) at a study visit should be discussed with the study designated physician.

Patient Reported Outcomes (PRO) Instruments (Questionnaires)

Subjects will complete the self-administered PRO instruments on the study visits specified in [Appendix C](#) and [Appendix D](#). Subjects should be instructed to follow the instructions provided with each instrument and to provide the best possible response to each item. Site personnel shall not provide interpretation or assistance to subjects other than encouragement to complete the tasks. Subjects who are functionally unable to read any of the instruments may have site personnel read the questionnaires to them. Site personnel should encourage completion of each instrument at all specified visits and should ensure that a response is entered for all items.

Short Form 36 – Version 2 Health Survey (SF-36v2)

The SF-36v2 is a general Health Related Quality of Life (HRQoL) instrument with extensive use broad variety of health conditions and is the standard in literature for HCV. The SF-36v2 instrument comprises 36 total items (questions) targeting a subject's functional health and well-being in 8 domains (physical functioning, role physical, bodily pain, general health, vitality, social functioning, role emotional and mental health). Domain scores are also aggregated into a Physical Component Summary score and a Mental Component Summary score. Higher SF-36v2 scores indicate a better state of health. The SF-36v2 should require approximately 10 minutes to complete.

Treatment Satisfaction Questionnaire-Medicine (TSQM)

The TSQM is a 14-item instrument and includes assessments of satisfaction with a medication's effectiveness (Effectiveness, three items), lack of side effects (Side Effects; five items), convenience (three items) and the subject's global satisfaction (Global Satisfaction; three items).

The subject should complete the questionnaire before site personnel perform any clinic assessments and before any interaction with the site personnel has occurred to avoid biasing the subject's response. TSQM scores range from 0 – 100 with higher scores indicating better satisfaction. The TSQM should require approximately 5 minutes to complete.

EuroQol-5 Dimensions-3 Level (EQ-5D-3L)

The EQ-5D-3L is a health state utility instrument that evaluates preference for health status (utility). The 5 items in the EQ-5D-3L comprise 5 dimensions (mobility, self-care, usual activities, pain/discomfort, and anxiety/depression) each of which are rated on 3 levels of severity. Responses to the 5 items encode a discrete health state which is mapped to a preference (utility) specific for different societies. Subjects also rate their perception of their overall health on a separate visual analogue scale (VAS). The EQ-5D-3L should require approximately 5 minutes to complete.

PRO instruments should be consistently presented so that subjects complete the questionnaires in the following order: the SF-36v2, TSQM, and EQ-5D-3L. PRO instruments should be completed prior to drug administration on Day 1 and prior to any discussion of adverse events or any review of laboratory findings, including HCV RNA levels, at all study specified visits listed in [Appendix C](#) and [Appendix D](#). The TSQM is the only PRO assessment that will not be performed at Day 1.

Enrollment and Assignment of Subject Numbers

All Screening activities must be completed and reviewed prior to enrollment. Subjects who meet all the Inclusion Criteria and none of the Exclusion Criteria at Screening will proceed to enrollment via the IRT system on Study Day 1.

Subject numbers will be unique 4 digit numbers and will begin with 1001 with the first two digits representing the investigative site, and the last two digits representing the subjects at that site. Enrolled subjects will keep their subject number throughout the study. Subjects will be enrolled on Study Day 1 as described in Section [5.5.4](#).

Study Drug Compliance for Kits

Individual bottles of GLE/PIB will be provided for subject dosing to the site. Each subject will have compliance documented by the site in the subject's source notes for GLE/PIB. At each Study Drug Accountability Visit in [Appendix C](#), the overall number of tablets of GLE/PIB remaining in each bottle will be recorded and entered in the IRT system along with the date of reconciliation.

Additional information regarding treatment compliance can be found in Section [5.5.6](#).

HCV Genotype and Subgenotype

Plasma samples for HCV genotype and subtype determination will be collected at Screening. Genotype and subtype will be assessed using the Versant® HCV Genotype Inno LiPA Assay, Version 2.0 or higher (LiPA; Siemens Healthcare Diagnostics, Tarrytown, NY) by the central laboratory. If the LiPA assay is unable to genotype a

sample, its genotype and subtype will be evaluated by a Sanger sequencing assay of a region of the NS5B gene by the central laboratory.

HCV RNA Levels

Plasma samples for HCV RNA levels will be collected as indicated in [Appendix C](#) and [Appendix D](#). Plasma HCV RNA levels will be determined for each sample collected by the central laboratory using the Roche COBAS® AmpliPrep/COBAS® TaqMan HCV Quantitative Test, v2.0. The lower limit of detection (LLOD) and lower limit of quantification (LLOQ) for this assay (regardless of genotype) are both 15 IU/mL.

HCV Resistance Testing Sample

A plasma sample for HCV resistance testing will be collected prior to dosing on Day 1 and at the study visits indicated in [Appendix C](#) and [Appendix D](#). Specific instructions for preparation and storage of HCV RNA and HCV resistance samples will be provided by the central laboratory, AbbVie, or its designee.

Study Drug Dosing Card

Subjects will be provided with self-administration instructions and study drug dosing cards to record the exact date, time (record to the nearest minute) and number of tablets of study drug administration (GLE/PIB) for the last 2 doses of study drug taken prior to the scheduled pharmacokinetic sample collection visits during the Treatment Period as detailed in [Appendix C](#).

The site staff will record the information about the last 2 doses taken prior to the scheduled pharmacokinetic sample collection from the study drug dosing card into the eCRF. In the event that the dosing card is not available, the site may obtain dosing information via patient interview and record this information in the source notes and the eCRF.

To facilitate proper dosing of study drug before pharmacokinetic evaluation blood samples are taken, the following procedures should be performed:

- The Investigator or designee should make sure the subject is given the dosing card at the visits listed in [Appendix C](#).
- The Investigator or designee will contact the subject approximately 2 days before the scheduled visit date to review the importance of proper study drug administration relative to the pharmacokinetic blood collection and documentation of dosing times on the dosing card. The date and time of the contact will be entered into the subject's source documents.
- The completed dosing card will be collected by the Investigator or designee on the day of the visit and be kept as a source record of dosage administration times documented in the eCRF.

Flow Cytometry, HIV RNA and HIV Resistance Testing Samples

For subjects with HCV/HIV coinfection, samples for plasma HIV RNA levels and flow cytometry (including but not limited to CD4+ T-cell and CD8+ T-cell counts [absolute and percent]) will be obtained at the times specified in [Appendix C](#) and [Appendix D](#).

Plasma HIV-1 RNA will be measured by the central laboratory using the Roche COBAS AmpliPrep/COBAS TaqMan HIV-1 Test, version 2.0 HIV-1 Assay. Results below the LLOD are reported as: "Not Detected."

If a HIV RNA level result of subject on stable HIV ART is ≥ 200 copies/mL, the subject's HIV RNA is to be repeated as noted in Section [5.4.1.2](#). At the time the repeat plasma HIV RNA is drawn, a sample should be obtained for HIV genotypic resistance testing. If the subject's repeat HIV RNA is ≥ 500 copies/mL, the sample obtained for HIV genotypic resistance testing will be analyzed.

HIV protease (PR), reverse transcriptase (RT) and integrase (IN) sequences, as applicable, will be analyzed by Monogram Biosciences using the GenoSure® Prime drug resistance assay.

If the subject's repeat HIV RNA is < 200 copies/mL, then the subject will resume routine plasma HIV RNA assessments as shown in [Appendix C](#) and [Appendix D](#), and described in Section [5.4.1.2](#).

Specific instructions for preparation and storage of flow cytometry, plasma HIV RNA, and HIV resistance samples will be provided by the central laboratory, AbbVie, or its designee.

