5.5 Treatments

5.5.1 Treatments Administered

Each dose of GLE/PIB will be dispensed in the form of film-coated co-formulated tablets at the visits listed in [Appendix C](#). Subjects will be instructed to take study drug at the same time every day with food. Please refer to Section [5.3.1.1](#) and Section [5.3.2.1](#) for more details.

GLE/PIB will be provided by AbbVie as 100 mg/40 mg film-coated tablets. GLE/PIB will be taken orally at GLE 300 mg/PIB 120 mg (three × GLE 100 mg/PIB 40 mg tablets) QD and with food.

Beginning with Study Day 1, the site will use the IRT system to obtain the study drug kit numbers to dispense at the study visits specified in [Appendix C](#). Study drug must not be dispensed without contacting the IRT system. Study drug may only be dispensed to subjects enrolled in the study through the IRT system. The site will also contact the IRT system to provide study drug return information for each kit at the visits specified in [Appendix C](#). At the end of the Treatment Period or at the Premature D/C Visit from the Treatment Period, the site will contact the IRT system to provide the discontinuation visit date information and study drug return information for each kit (Section [5.5.7](#)).

All subjects who receive at least one dose of study drug and meet the HCV virologic failure criteria defined in Section [5.4.1.1](#) will be discontinued from treatment.

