11.3.2 Statistical Methods

The baseline value for clinical laboratory tests will be the last non-missing measurement on or before the day of the first dose of study drug. Values on Day 1 must also be before the time of first dose if time is available. The same baseline value will be used for changes at Treatment Period visits and changes at Post-Treatment Period visits.

Changes from baseline to each post-baseline visit, including applicable post-treatment visits, will be summarized. Each protocol-specified laboratory parameter will be summarized with the sample size, baseline mean; visit mean; and change from baseline mean, standard deviation, minimum, median, and maximum.

Individual changes in the laboratory parameters listed in Section 11.3.1 will be tabulated using shift tables. Laboratory data values will be categorized as low, normal, or high based on normal ranges of the laboratory used for each sample. Shift tables from baselineto minimum value and maximum value during the Treatment Period will be created. For each parameter, the shift tables will cross tabulate the frequency of subjects with baseline values below/within the normal range to maximum above the normal range and with baseline values within/above the normal range to minimum below the normal range.

The laboratory parameters listed in Table 11 will be assigned a toxicity grade of 1, 2, 3, or 4. The number and percentage of subjects with a maximum toxicity grade of 1, 2, 3 or 4 will be tabulated. To be counted, the post-baseline value must have a toxicity grade that is more extreme than the toxicity grade corresponding to the baseline value. For each laboratory parameter in Table 11, the summary will also include the number and percentage of subjects with a maximum of at least grade 3. A listing of all relevant laboratory parameters will be provided for each subject who had an increase to grade 2 or higher for any laboratory variable in Table 11.

Assessment of Hepatic Laboratory Values

The number and percentage of subjects with laboratory values meeting the following criteria during treatment will be summarized:

- Post-nadir (preceding value is lower than the subsequent value) ALT $> 5 \times \text{ULN}$ (regardless of grade change);
- Total bilirubin $\geq 2 \times \text{ULN}$ and $>$ baseline (i.e., a post-baseline value must be more extreme than the baseline value to be considered);
- Post-nadir ALT $> 3 \times \text{ULN}$ and total bilirubin $> 2 \times \text{ULN}$;

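### Fasting status is recorded but not used in the SAP, so fasting and non-fasting glucose can be compared and a meal-related rise can be counted as a worsened grade

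*Protocol*

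**What the plan says.** **Collection (Protocol 5.3.1.1, Clinical Laboratory Tests).** The general rule is: "Blood samples for serum chemistry tests should be collected following a minimum 8-hour fast prior to study drug intake". One visit is exempt: "with the exception of the Screening Visit, which may be non-fasting". The footnotes to Appendix C repeat both statements. For Day 1: "At the Study Day 1 visit, a fasting blood sample should be collected prior to the first dose of study drug". For later visits held after dosing: "Subjects whose visits occur following the morning dose of study drug should be instructed to fast after breakfast until the study visit occurs". That sentence gives no number of hours. Protocol 5.5.1 adds: "Subjects will be instructed to take study drug at the same time every day with food". If the fast was missed, the instruction is: "Blood samples should still be drawn if the subject did not fast for at least 8 hours". Whether the subject fasted is noted in the source documents and on the laboratory requisition. The eCRF and the analysis database are not mentioned.

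**Analysis (SAP 11.3 to 11.3.2).** All central and local laboratory results enter all analyses, including extra tests prompted by a serious adverse event. Baseline is the last non-missing value on or before the first dosing day, with no fasting condition. Table 10 grades high glucose from just above the ULN (Grade 1, up to 8.9 mmol/L) to above 27.8 mmol/L (Grade 4), with no fasting qualifier. Each subject's maximum grade is tabulated, under this rule: "To be counted, the post-baseline value must have a toxicity grade that is more extreme than the toxicity grade corresponding to the baseline value". The SAP text does not mention fasting in any filter, stratification, listing or sensitivity analysis.

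**The concern.** Glucose depends on recent food, which is presumably why the protocol sets a fasting rule and records whether it was met. The analysis then ignores that record. Under the schedule, the Day 1 baseline is meant to be fasting, while a follow-up sample can come from a subject who took the drug with breakfast that morning or who missed the fast. Comparing the two on one grading scale mixes a meal effect with any drug effect.

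Two features of the plan add to this. The grade table takes the maximum over samples, so one unfasted value is enough to count a subject. And there is no control arm in which the same meal effect would appear. Safety is part of the primary objective (Protocol 4.1), and with about 100 subjects each misgraded subject moves the table by 1/100, or 1 percentage point. A reader who sees several raised glucose grades could not tell meals from a signal.

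**Working it through.** The plan states no figure for glucose grades or for unfasted samples, so there is nothing to reproduce. The check is a comparison of texts, followed by an illustration.

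**1. Can a follow-up sample be non-fasting?** Yes. The 8-hour rule applies, but unfasted samples are kept. The instruction for post-dose visits would also be met by a subject seen a few hours after breakfast. A subject sampled at least 8 hours after breakfast satisfies both instructions.

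**2. Is the baseline fasting?** It is planned to be, but this is not guaranteed. The sentence on drawing unfasted samples is not limited to follow-up, so it also covers Day 1. If Day 1 glucose is missing, the SAP falls back to the last earlier value, which may be a Screening sample that was allowed to be non-fasting.

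**3. What happens in the grade table?**
- Fasting baseline within range, post-meal follow-up above the ULN: Grade 0 becomes Grade 1 or higher, and the subject is counted.
- Unfasted baseline already at Grade 1, fasting follow-up truly raised to Grade 1: no worsening in grade, and the subject is not counted.

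The first case follows from the planned schedule; the second needs a departure at baseline. The net direction is therefore mainly upward, but not in every subject.

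**4. Illustrative size.** From the documents: about 80 subjects in Arm A with two on-treatment chemistry samples (Week 4, end of treatment) and about 20 in Arm B with three (Weeks 4 and 8, end of treatment). Assumed, because the documents are silent: the share of samples unfasted, *u* (5% to 50%); the chance that an unfasted sample raises the grade, *q* (5% to 30%); independence between samples; and a fasting baseline. With *m* = *u* × *q*, the expected number of subjects counted because of meals alone is

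80 × [1 − (1 − *m*)²] + 20 × [1 − (1 − *m*)³]

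| *u* | *q* | *m* | Arm A | Arm B | Total of 100 |
|---|---|---|---|---|---|
| 5% | 5% | 0.0025 | 0.40 | 0.15 | 0.55 |
| 10% | 10% | 0.01 | 1.59 | 0.59 | 2.19 |
| 25% | 20% | 0.05 | 7.80 | 2.85 | 10.65 |
| 50% | 30% | 0.15 | 22.20 | 7.72 | 29.92 |

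Adding the Post-Treatment Week 4 sample (three and four samples) gives 0.80, 3.16, 15.12 and 40.43. If every sample is fasting, *u* = 0 and the count is 0. The width of this range shows that the documents cannot settle the size.

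**The case against.** The case for leaving the plan alone has several parts.

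- **The 8-hour fast is the rule.** A reader might infer from the post-breakfast instruction that follow-up samples need not be fasting. The documents do not support that: the minimum applies at every visit except Screening, and the looser sentence stands in the same paragraph. Unfasted samples are tolerated departures. This stands, and it limits the point to what can happen.
- **The bias need not run one way.** This also stands, for the baseline reasons above. It does not rescue the analysis, since it means that the two kinds of value can be mixed on both sides of the comparison.
- **The stakes are small.** Grade 1 starts just above the ULN. The SAP separately summarises Grade 3 or higher, which for glucose means above 13.9 mmol/L, and nothing in the documents suggests that meals alone would reach it. Subjects with an increase to Grade 2 or higher are listed. Glucose is not an adverse event of special interest (SAP 11.2.3), and a laboratory value becomes an adverse event only under the conditions in Protocol 6.1.1.1. All of this stands and keeps the priority low. The listing, however, is not said to show fasting status, so it would not by itself separate meals from drug.
- **Using all values is the cautious choice for safety.** This is fair as far as it goes: a restriction that removed high values from view would be worse than pooling. The fix must therefore keep every value visible.

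**Conclusion.** The point holds as a low-priority improvement. The protocol records fasting status, the SAP pools glucose without it, and the maximum-grade rule allows one unfasted sample to count a subject as worsened. Under the planned fasting baseline the error is mainly toward too many high-glucose grades; with an unfasted baseline it can mask a true rise.

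The size is unknown. The range of about 0.55 to about 30 of 100 subjects rests entirely on assumed rates of unfasted sampling and of meal-related grade rises.

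A reader might go further and conclude that meal effects will inflate the table in one direction, or that the plan would report them as treatment-emergent events. The documents support neither. Departures from fasting may be few or absent, baseline values can be affected too, and the SAP describes these laboratory results only as grades worse than baseline.

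**What to change.** 1. In SAP 11.3.2, state that the glucose mean-change, shift and toxicity-grade summaries compare a fasting baseline with fasting post-baseline values.
2. Show non-fasting glucose, including local and serious-adverse-event samples, in a separate row and listing, so that no value is dropped. Subjects without a fasting baseline should appear there too.
3. Confirm that the fasting flag on the requisition is transferred to the analysis data. The protocol does not say that it is.
4. Reconcile the 8-hour rule with the post-breakfast instruction in Protocol 5.3.1.1, so that sites know when a sample is to be recorded as fasting.
5. While editing SAP 11.3.2, correct its pointer for laboratory grades: it cites Table 11, which holds vital-sign criteria, whereas the grades are in Table 10.

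The cost is a short SAP edit, a data-transfer check and fewer values in the main glucose row. No new data are collected. If the flag cannot be recovered from the requisition data, it would have to come from source documents, or the limitation would have to be stated beside the table.
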